#### 14.5 Overall Survival

Overall Survival (OS) is defined as the time from treatment start to the date of death, regardless of the actual cause of the subject's death. For subjects who are still alive at the time of the data cut-off for the analysis or who are lost to follow up, OS time will be censored at the last recorded date that the subject is known to be alive as specified in Section 9.4.

OS (in months) = (Date of death – Date of first study treatment administration +1) / 30.4375

Kaplan-Meier (i.e., product-limit) estimates of median OS time will be presented by cohort dose level together with two-sided 95% CIs calculated according to Brookmeyer and Crowley (1). The number of subjects at risk vs. failed along with Kaplan-Meier estimates of survival probability at 3, 6, and 12 months (as well as further timepoints as appropriate) will be estimated with corresponding two-sided 95% CIs derived using the log-log transformation according to Kalbfleisch and Prentice (2) (i.e., CONFTYPE=loglog default option in SAS LIFETEST procedure). The estimate of the standard error will be computed using Greenwood's formula.

Frequency (number and percentage) of subjects with an event (death) and censoring reasons will also be presented by treatment arm. Censoring reasons are as follows:

- Ongoing in the study without an event
- Withdrawal of consent
- Lost to follow-up

The OS time or censoring time and the reasons for censoring will also be presented in a subject listing.

# 15 Safety Analyses

The subsections in this section include specifications for summarizing safety endpoints that are common across clinical trials such as AEs, laboratory tests and vital signs.

#### 15.1 Adverse Events

Analysis set: SAF

The severity of AEs will be graded using the National Cancer Institute – Common Terminology Criteria for Adverse Events (NCI-CTCAE) v5. If a particular AE's severity is not specifically graded by this guidance, the Investigator uses the general NCI-CTCAE definitions of Grade 1 through Grade 5 following his or her best medical judgment. The latest MedDRA version at the time of data cut-off will be used to code AEs according to SOC and PT.

- Treatment Emergent Adverse Events (TEAEs) are events with onset dates occurring during the on-treatment period, or those that worsen in severity during the on-treatment period. All analyses will be based on TEAEs unless otherwise specified.
- Related Adverse Events have a relationship to study treatment of "Related", or missing relatedness, as reported by the Investigator on the "Adverse Events Details" eCRF page. Relatedness is defined separately for each study intervention component.
- Serious Adverse Events (SAEs) are those recorded on the "Adverse Events Details" eCRF
  page as Serious Adverse Event = "Yes".
- Adverse Events Leading to Treatment Discontinuation are those recorded on the "Adverse Events Details" eCRF page as Action(s) taken with M3814/ avelumab/ radiotherapy = "Drug withdrawn".
- Adverse Events Leading to Death are those recorded on the "Adverse Events Details" eCRF page as Outcome = "Fatal" as well as AEs of Grade 5.
- Adverse Events of Special Interest (AESIs) for this study include infusion related reactions (IRRs) / hypersensitivities and immune-related AEs (irAEs) / autoimmune disorders. IRRs and irAEs are identified based on a list of MedDRA PTs and other qualifying criteria, as specified in Appendix I.

Details on the handling of incomplete AE-related dates are specified in Section 9.4.

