4.1.1.3 Follow-Up Periods

Safety Follow-up

Part A, Part B, and Part FE

The Safety Follow-up period will be 30 days and 90 days after the last dose of avelumab for safety evaluation of the combination of study interventions.

Part B

In addition to the Safety Follow-up relating to the combination of study interventions after the last dose of avelumab, for Part B, the following RT Safety Follow-up periods are defined to assess potential toxicity of RT when administered in combination with M3814 and avelumab:

- Short-term RT Safety Follow-up: 30 days after the end of RT for evaluation of safety.
- Mid-term RT Safety Follow-up: 3 months after the end of RT to evaluate late signs of RT-induced toxicity on normal surrounding tissues.
- Long-term RT Safety Follow-up: 12 months after the end of RT, to evaluate RT-induced toxicities, by telephone call.

Long-Term Follow-up

Part A, Part B, and Part FE

Participants will be followed for survival and use of subsequent anticancer therapy until the end of the study. Participants without PD who are not receiving subsequent anticancer therapy after the End of Treatment Visit, will be followed every 8 weeks with radiographic disease evaluation for the first 6 months of the study and then every 12 weeks thereafter until PD according to Response Evaluation Criteria in Solid Tumors Version 1.1 (RECIST v 1.1), and for survival and use of subsequent anticancer therapy until the end of the study.

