6.6.4 Dose Escalation Rules

The criteria for dose escalation are based on the occurrence of AEs and/or DLTs during the DLT period in evaluable participants in each cohort. The DLT assessment period of 3 weeks (Part A) or 4 weeks (Part B) after the start of M3814 treatment allows an evaluation of acute toxicity. M3814 dose escalation will not proceed to the next dose level until the SMC has decided to escalate. Moreover, RT and the combination of RT and M3814 and avelumab can also give rise to later toxicities, especially radiation toxicities. A 30-day and 90-day Safety Follow-up will be performed in all participants in both Parts (A and B) of the study. Once available, these data, alongside with emerging safety, PK, and Pd data from the ongoing clinical projects involving M3814, will also guide subsequent dose escalation and the establishment of the RP2D. Furthermore, RT Safety Follow-up Visits will be performed in all participants in Part B 1 month (Short-Term RT Safety Follow-up), 3 months (Mid-Term RT Safety Follow-up), and 12 months (Long-Term RT Safety Follow-up, by telephone) after the last RT treatment, to assess any late RT toxicity. These data will be considered in determining the safety profile of the treatment combination.

Dose Escalation Part A (M3814 + avelumab 800 mg Q2W)

A Bayesian two-parameter logistic regression model with overdose control will be used to assist the SMC with dose selection during the Part A dose escalation. Cohorts of at least 3 participants each will be treated at the same dose level of M3814 (starting dose: 100 mg tablet formulation, BID) in combination with avelumab. On the day of avelumab administration, M3814 can be given prior to the start or just after the end of avelumab infusion. The model incorporates available clinical data and observed data from each completed cohort (and data from all previous cohorts) to provide a recommended dose for the next cohort. A preselected set of

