Adverse events observed from the first dose until 30 days after last study intervention administration (i.e. TEAEs) will be summarized according to MedDRA system organ classes and preferred terms. The incidence and type of the following will be analyzed:

- TEAEs and SAEs
- TEAEs and SAEs related to study intervention
- TEAEs with NCI-CTCAE Grades ≥ 3
- TEAEs related to study intervention with NCI-CTCAE Grades ≥ 3
- AEs leading to withdrawal, dose modifications, or permanent study intervention discontinuation
- Deaths.

Participants who terminate treatment will be displayed in a by-participant listing and summarized by primary withdrawal reason.

All reported deaths after first dose of study intervention as well as reasons for death will be tabulated (for all participants enrolled). Deaths within 30 days from last dose administration and deaths beyond this period up to 90 days follow-up and reasons for them will also be tabulated.

Laboratory Variables

Laboratory results will be classified by grade according to NCI-CTCAE v 5.0. The worst on-study grades after the first study intervention will be summarized.

Shifts in toxicity grades from first treatment to highest grade will be displayed. Results for variables that are not part of NCI-CTCAE will be presented as below, within, or above normal limits. Only participants with postbaseline laboratory values will be included in these analyses.

Physical Examination

Physical examination, including vital signs (body temperature, respiratory rate, heart rate, and blood pressure), and 12-lead ECG, recorded at Baseline and after administration of study intervention will be presented.

Further details will be provided in the Integrated Analysis Plan.

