### Part B:

Objectives	Endpoints (Outcome Measures)	IAP section
Primary		
To determine a safe, tolerable, RP2D and/or the MTD of M3814 when given in combination with avelumab and radiotherapy.	Occurrence of DLTs	15.1
Secondary		
To evaluate the safety profile and tolerability of M3814 in combination with avelumab and radiotherapy.	Occurrence of treatment-emergent adverse events and treatment-related adverse events according to the NCI-CTCAE v 5.0, and serious adverse events     Occurrence of abnormalities (Grade ≥ 3) in laboratory test values, markedly abnormal vital sign measurements, markedly abnormal physical examination measurements, clinically significant abnormal ECG, marked changes in ECOG PS     Incidence, severity and outcomes of RT-induced toxicity	15.2 – 15.6
To characterize the pharmacokinetics of M3814 and avelumab when given in combination with radiotherapy.	
 
Pharmacokinetic profile of avelumab in terms of pharmacokinetic parameter estimates, as feasible (eg, Cmax, Cmin, Racc[Cmax], Racc[AUC] and t1/2)
 
Pharmacokinetic profile of M3814 in terms of pharmacokinetic parameter estimates (Cmax, tmax, Cmin, Cavg, fluctuation index, AUCo-t, AUCo-v, Racc[Cmax], Racc[AUC], t1/2, Vz/f, CL/f, and Λz)
 
	16.1
To evaluate the immunogenicity of avelumab in combination with M3814 plus radiotherapy.	Immunogenicity as measured by ADA	16.3
To evaluate the preliminary antitumor activity of M3814 when	Confirmed BOR according to RECIST v 1.1, as assessed by the Investigator	14.1
given in combination with avelumab and radiotherapy in participants with	Confirmed DOR according to RECIST v 1.1, as assessed by the Investigator	14.2

Objectives	Endpoints (Outcome Measures)	IAP section
locally advanced and advanced solid tumors	PFS time according to RECIST v 1.1, as assessed by the Investigator	14.4
	Tumor size measurement based on Investigator assessment according to RECIST v 1.1	14.3
	Overall Survival	14.5
CCI		

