### Definition of on-treatment period

The on-treatment period is defined as the time from the first dose of study treatment through the minimum of (last date of study intervention + 30 days, start day of new anti-cancer drug therapy - 1 day, death).

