#### 15.2.3 Serious Adverse Events

Analysis set: SAF

Please refer to Section 15.1.1 for details on SAE summaries.

The listings of all SAEs will also be provided with the relevant information with a flag for SAEs with onset outside of the on-treatment period.

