# 15.2.4 Adverse Events of Special Interest

Analysis set: SAF

The frequency (number and percentage) of subjects with each of the following will be presented for treatment emergent irAEs, by dose level:

- irAEs leading to death, by SOC and PT
- irAEs, by SOC and PT
- irAEs leading to discontinuation, by SOC and PT
- irAEs, Grade ≥ 3, by SOC and PT
- irAEs by SOC and PT and worst grade
- Serious irAEs by SOC and PT

The listing of all irAEs will also be provided with the relevant information with a flag for irAEs with onset outside of the on-treatment period. A separate listing of irAEs with onset after the ontreatment period will also be provided.

The frequency (number and percentage) of subjects with each of the following will be presented for treatment emergent IRRs, by dose level:

- IRRs leading to death, by SOC and PT
- IRRs leading to discontinuation, by SOC and PT
- IRRs, by SOC and PT
- IRRs, Grade ≥ 3, by SOC and PT
- Serious IRRs, by SOC and PT

Timing of first onset of an IRR (infusion 1, infusion 2, infusion 3, infusion 4 or later) will be provided.

The listing of all IRRs will also be provided with the relevant information with a flag for IRRs with onset outside of the on-treatment period.

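### Part B radiotherapy toxicity that starts after the treatment-emergent window enters no adverse event incidence or grade table, although it is a secondary endpoint with 3- and 12-month follow-up visits

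*SAP*

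**What the plan says.** - **Endpoint.** SAP Section 5 lists "Incidence, severity and outcomes of RT-induced toxicity" as a Part B secondary endpoint. Protocol 9.4.2 also names RT-induced toxicity as an item for descriptive tabulation.
- **Default rule.** SAP 15.1: "All analyses will be based on TEAEs unless otherwise specified". A TEAE starts or worsens during the on-treatment period.
- **Window.** SAP 9.1 ends that period at the "minimum of (last date of study intervention + 30 days, start day of new anti-cancer drug therapy - 1 day, death"). Protocol 9.4.2 has the same 30-day limit ("Adverse events observed from the first dose until 30 days after last study intervention administration (i.e. TEAEs") but no cut at new therapy. SAP Section 7, which records changes from the protocol, does not mention the added cut.
- **Follow-up.** Protocol 4.1.1.3 sets RT safety visits at 30 days, 3 months and 12 months after RT, including "Long-term RT Safety Follow-up: 12 months after the end of RT, to evaluate RT-induced toxicities". Protocol 6.6.4 says of the RT follow-up findings: "These data will be considered in determining the safety profile of the treatment combination".
- **Events after the window.** SAP 15.2.4 makes special provision for immune-related events: "A separate listing of irAEs with onset after the ontreatment period will also be provided". SAP 15.2.3 gives the SAE listing "a flag for SAEs with onset outside of the on-treatment period". RT toxicity gets no corresponding output.

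**The concern.** The treatment-emergent window is tied to avelumab, whereas the toxicity comes from RT that ends on Day 12. Protocol Appendix 8 calls RT effects late when they appear more than 3 months after RT. A participant who stops avelumab early leaves the window before late effects can start, yet remains under RT follow-up meant to find them. Protocol Table 3 foresees this case: if avelumab has stopped before the 12-month RT visit, that visit can be done by telephone. The information is collected and then left out of the tables that report incidence and grade.

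Two consequences follow. The Part B tables understate late RT toxicity, because events outside the window are not counted. And dose-level columns with different avelumab durations cover late toxicity to different extents.

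**Working it through.** **Step 1. Which safety outputs could count an RT-related event that starts after the window?**

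| SAP output | Limited to the window? | What it gives for late RT toxicity |
|---|---|---|
| RT-related TEAE tables by SOC/PT and by worst grade (15.1.1) | Yes | Nothing after the window |
| Listing of all AEs (15.1.1) | No | Individual rows only |
| SAE listing (15.2.3) | No, flagged | Individual rows, serious events only |
| Deaths by primary reason (15.2.2) | No | Fatal events only |
| DLT tables (15.2.1) | First 28 days | Nothing late as defined |
| irAE tables (15.2.4) | Yes | Not an RT output |

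No table of incidence or grade remains. The outcome part of the endpoint is not tabulated beyond discontinuation and death. SAP Section 5 refers this endpoint to SAP 15.2 to 15.6. Those sections contain no RT-toxicity analysis, and the SAP has no Section 15.6.

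**Step 2. Date thresholds, from the documents.** Inputs: the last fraction is on Day 12; avelumab is given on Days 1, 15, 29 and so on (Day 1 + 14k); RT visits are on Day 99 and Day 351 (Protocol Table 3). An onset counts only if

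last dose day ≥ onset day − 30.

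The earliest late onset, with 3 months taken as 91 days, is 12 + 91 + 1 = Day 104. Protocol Appendix 8 puts the average onset of late radiation esophagitis at 6 months. Counted from the last fraction (an assumption), that is 12 + 183 = Day 195.

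| Onset day | Last dose needed on or after | First planned infusion that qualifies |
|---|---|---|
| 99 | 69 | 6th, Day 71 |
| 104 | 74 | 7th, Day 85 |
| 195 | 165 | 13th, Day 169 |
| 351 | 321 | 24th, Day 323 |

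For example, a participant who stops at the Day 56 scan has a last dose on Day 43 or 57. The window then closes on Day 73 or 87, before both later RT visits.

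**Step 3. Share of participants still in the window (assumption).** The documents give no avelumab duration. Assume exponential time to last dose with median m months, and ignore new therapy:

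P(last dose ≥ d) = 0.5^(d / (30.4375 m)).

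For d = 69 and m = 2: 0.5^(69/60.875) = 0.456.

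| Onset day (d) | m = 2 | m = 3 | m = 4 | m = 6 |
|---|---|---|---|---|
| 99 (69) | 46% | 59% | 68% | 77% |
| 104 (74) | 43% | 57% | 66% | 75% |
| 195 (165) | 15% | 29% | 39% | 54% |
| 351 (321) | 3% | 9% | 16% | 30% |

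Half or more are outside the window when the median is below d/30.4375: about 2.3 months for Day 99, 5.4 for Day 195 and 10.5 for Day 351.

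**Step 4. Restricted to participants still alive (assumption).** Suppose a share f of avelumab stops are deaths, with the same death hazard on and off treatment. The exponent is then multiplied by (1 − f). With f from 0.2 to 0.4 and m from 2 to 6, coverage is 53% to 86% on Day 99, 22% to 69% on Day 195 and 5% to 48% on Day 351.

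**The case against.** The strongest case against is about weight. Part B expects 6 to 24 participants, 3 to 6 per dose level, in an exploratory study with no hypotheses. Every AE is listed, so nothing is lost, and with columns this small a table may say little more than the listing. The 30-day limit is the protocol's own. The SMC may label late in-field radiation toxicity a DLT at any time, and its outputs are set out in a charter that is not part of these documents. No formal comparison of dose levels is planned, and duration of therapy is summarized by dose level, so unequal windows can be seen.

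The small size and the listings do lower the stakes. But a listing does not give incidence by grade and dose level, which the endpoint asks for, and in columns of 3 to 6 one uncounted event changes the rate visibly. Sharing the 30-day rule with the protocol does not provide the separate RT-toxicity tabulation that Protocol 9.4.2 also names.

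Other objections stand as limits:
- The percentages are assumptions, and no late-event rate is given, so the understatement has no size in events.
- Day 99 is only 87 days after RT, which is still acute under Appendix 8.
- Acute toxicity is better covered: a participant who completes RT on Day 12 is in the window to at least Day 42, absent new drug therapy or death.
- AE assessment at the general long-term follow-up is not required once new antitumor treatment starts, so part of that loss arises at collection. The RT safety visits carry no such exemption.
- Palliative RT outside the study fields, permitted after the DLT period, can blur attribution.

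**Conclusion.** The concern holds. Under the SAP as written, RT-related events that start after the treatment-emergent window appear in no AE incidence or grade table, and counting a late event depends on when avelumab stopped. This conclusion rests on the text and on the date thresholds: last dose on or after Day 69 for a Day 99 onset, and on or after Day 321 for Day 351. It does not need the modelled percentages, which only illustrate that coverage could be well under half by 12 months if median time on avelumab is 2 to 6 months. The gap should be closed before database lock, but it does not threaten the primary endpoint.

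**What to change.** Add to SAP Section 15, for Part B only, one table and one listing of RT-related AEs with onset from the first RT fraction to the end of AE collection, including the 12-month RT visit. Do not cut them at last dose + 30 days or at new therapy.

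- Tabulate by PT, worst grade and outcome, by dose level.
- Split into acute and late, with the boundary stated in days from the last fraction given. This must be explicit: the Day 99 ± 7 visit falls 80 to 94 days after a Day 12 fraction, across a 91-day boundary, and Protocol 4.1.1.3 assigns that visit to late signs.
- Flag events that start after new anticancer therapy or after non-study palliative RT.
- Show the number of participants alive and followed at each RT visit.

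The existing TEAE tables can stay as they are. The cost is the programming of one table and one listing, because AE assessment is already scheduled at all RT safety visits. The drawbacks are confounding by later therapy and incomplete collection after new treatment starts. The flags and follow-up counts make both visible.

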#### 15.1.1 All Adverse Events

Adverse events will be summarized by worst severity per subject, using MedDRA PT as event category and SOC as summary category, in alphabetical order. If an AE is reported for a given subject more than once during treatment, the worst severity and the worst relationship to study treatment will be tabulated.

An overall summary table of AEs will be prepared and will tabulate the number and percentage of participants with AEs in the following categories:

- Any TEAE
- TEAEs related to study intervention (tabulated by relatedness to any study intervention, and individual study intervention components)
- Any serious TEAEs
- Serious TEAEs related to study intervention (tabulated by relatedness to any study intervention, and individual study intervention components)
- TEAEs with NCI-CTCAE severity Grade ≥ 3
- TEAEs related to study intervention with NCI-CTCAE severity Grade ≥ 3 (tabulated by relatedness to any study intervention, and individual study intervention components)
- TEAEs leading to death
- TEAEs related to study intervention leading to death (tabulated by relatedness to any study intervention, and individual study intervention components)
- Treatment-emergent AESIs overall and by category (see Section 15.2.4 for more details on summaries of AESIs)

In addition, tables summarizing the frequency of subjects with AEs, presented by SOC and PT, in the following categories will be prepared. Tables summarizing TEAEs related to study intervention will be created to summarize TEAEs related to any study intervention and will be repeated to summarize TEAEs related to specific study intervention components (M3814, avelumab, and, for Part B, RT).

- Any TEAE
- TEAEs by worst grade
- TEAEs related to study intervention
- Serious TEAEs
- Serious TEAEs related to study intervention
- TEAEs related to study intervention by worst grade
- TEAEs leading to death
- TEAEs related to study intervention leading to death

#### Clinical trial.gov and EudraCT requirements

Summary tables for nonserious AEs, applying frequency threshold of 5% in any dose level when excluding SAEs, by SOC and PT, will be provided.

Details of the AESIs will be presented in a listing sorted by SOC and PT, including: Subject number, SOC, PT, AESI category, relationship to avelumab, seriousness, grade, start date, cohort dose level, and time since last and first administration of avelumab.

A listing of all AEs will also be prepared, including all relevant details from the "Adverse Events Details" eCRF page. A flag will be included in the listing, identifying AEs attributed to COVID-19.

# 15.1.2 Adverse Events Leading to Study Intervention Discontinuation

An overall summary table of AEs leading to permanent study intervention discontinuation will be prepared and will tabulate the number and percentage of participants with AEs in the following categories:

- Any TEAE leading to permanent discontinuation of at least one study intervention
- TEAEs leading to permanent discontinuation of M3814
- TEAEs leading to permanent discontinuation of avelumab
- TEAEs leading to permanent discontinuation of RT (Part B only)
- TEAEs leading to permanent discontinuation of both M3814 and avelumab
- TEAEs related to M3814 leading to its permanent discontinuation
- TEAEs related to avelumab leading to its permanent discontinuation
- TEAE related to both leading to permanent discontinuation
- TEAEs related to RT leading to its permanent discontinuation
- AESIs leading to permanent discontinuation of avelumab, by category

In addition, tables summarizing the frequency of subjects with TEAEs, presented by SOC and PT, in the following categories will be prepared.

- TEAEs leading permanent discontinuation of avelumab
- TEAEs leading permanent discontinuation of M3814
- TEAEs leading permanent discontinuation of RT (Part B only)
- TEAEs leading permanent discontinuation of M3814 and avelumab
- TEAEs related to avelumab leading to its permanent discontinuation
- TEAEs related to M3814 leading to its permanent discontinuation

As action taken with study intervention will be detailed in the full listing of AEs, no separate listing of AEs leading to permanent discontinuation of study intervention will be produced.

